4.2.6.3 Health related quality life: SNOT-22 score

For the total score and individual item, SNOT-22 scores and changes from baseline will be summarised by treatment group and by time point using descriptive statistics for all patients in the PFAS. The change from baseline in the SNOT-22 total score will be analysed using a similar ANCOVA analysis as the primary endpoints described in Section 4.2.5.1. Results will be presented in terms of LSMEANS, treatment differences in LSMEANS, 95% CI and p-values for all time points.

Responder analyses at Week 24 and Week 56, where a responder is defined as change from baseline ≤ -8.9 , will be conducted using the same logistic regression model mentioned in Section 4.2.5.4. The results of the analyses will be presented using odds ratio, together with associated 95% CI and 2-sided p-value.

Subgroup analyses as mentioned in Section 4.2.5.3 will also be conducted for the change from baseline in SNOT-22 total score, including the subgroup analysis by PK exposure quartile.

The cumulative distribution function of absolute changes from baseline in SNOT-22 total score at Week 24 and at Week 56 will also be plotted in figures.

4.2.7 Other secondary efficacy variables

All other secondary efficacy endpoints will be collected during the double blinded period according to the SoA Table 2 in the CSP, except surgery and SCS use for CRSwNP will be further collected during the OLE period (CSP Table 3). Therefore following analyses specified in Section 4.2.7.1 and 4.2.7.6 only apply to the double blind period at the primary DBL. Surgery and SCS use for CRSwNP during the OLE period will descriptively summarized at final DBL.

4.2.7.1 Time to first surgery and/or SCS use for CRSwNP

At the primary DBL, the time to first surgery for CRSwNP, time to first course of SCS use for CRSwNP, and the time to first surgery or first course of SCS use for CRSwNP during the DB period will be analysed using a Cox proportional hazards model with treatment arm, region, CCI as covariates. Double blind period defined in Section 3.1.1 (as opposed to the target Day 393 for Week 56) will be used such that events (if any) reported after Day 393 but before the Visit 11 completion (or the first OLE dose) can be included in the respective time-to-event analysis. Results will be summarised as hazard ratios, 95% CI and p-values. Time to event will be displayed graphically using a Kaplan-Meier plot.

As another supportive analysis, the time to decision to have surgery for CRSwNP will be analysed using the same Cox proportional hazards model.

At the final DBL, additional descriptive summary will be provided for events reported during the OLE period; Cox proportional hazards model will not be conducted.

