4. STUDY DESIGN

4.1. Overall design

This is a randomised, double-blind, placebo-controlled, parallel-group, multicentre, Phase 3 study to evaluate the efficacy and safety of repeat dosing of benralizumab 30 mg administered SC versus placebo in patients with severe eosinophilic CRSwNP. Following completion of the double-blind period, patients have the option to enter an OLE.

Approximately 250 patients will be randomised, to receive benralizumab 30 mg SC or matching placebo.

Patients will be stratified by region and baseline CCI. Randomisation will be monitored to ensure that no more than CCI of the study population will have CCI. When the target percentage of patients in a subgroup is reached, consideration will be given to closing the IWRS randomisation for that subgroup. Once a subgroup is closed, patients in the screening/run-in period in the closed subgroup will not be allowed to be randomised and will be screen failed.

After enrolment, and prior to entering the screening/run in period, eligible participants will have their current INCS therapy switched to MFNS (400 mcg daily) or equivalent (highest local approved for CRSwNP), which should be maintained throughout the study until the last DB visit (V11). Patients must have been on a stable daily dose of INCS for at least 4 weeks prior to V1. Patients will be provided with an electronic patient-reported outcome (ePRO) device to record symptoms throughout the study until V11 (week 56) (see section 8.1.1 Clinical outcome assessments).

Patients who continue to meet eligibility criteria will be randomised 1:1 at Visit 3 (Day 0) to receive either placebo or benralizumab 30 mg SC every 4 weeks for the first 3 doses (Weeks 0, 4 and 8) and every 8 weeks thereafter (Weeks 16, 24, 32, 40 and 48). All patients who complete the 56-week DB treatment period on IP may be eligible to continue into an OLE, during which all patients will receive 8 doses of benralizumab 30 mg every QW4 for the first 3 doses (Weeks 56, 60, 64) and Q8W thereafter (Weeks 72, 80, 88, 96 and 104). Patients randomized to the Benralizumab arm during DB period will receive one dose of placebo (dummy) injection at Visit 12 (week 60) in order to maintain the blind.

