9.4.1.2. Methods for efficacy analyses

Analyses of the co-primary endpoints

The primary estimand will be applied to the co-primary endpoints, the change from baseline in total NPS and the change from baseline in NBS, using a hybrid method of the worst-possible/worst-observation carried forward and multiple imputation, followed by an analysis of covariance with treatment arm, baseline scores of corresponding endpoint, region, and baseline CCI status (CCI) as covariates. The estimates of the treatment effects at Week 56 will be based on a contrast from this ANCOVA model. The analyses will use the data collected up to Week 56 visit regardless of whether patients remained on treatment or not

except data collected after CRSwNP surgery and/or SCS use for CRSwNP. A composite strategy will be used for CRSwNP surgery and SCS use for CRSwNP. If a patient had any CRSwNP surgery or course of SCS use for CRSwNP before Week 56, the data will be censored before the first CRSwNP surgery and/or the time of having the first course of SCS use for CRSwNP, and the patient's worst-possible/previously worst-observed value will be imputed in its place.

Sensitivity analyses will be conducted based on different estimands and different missing data mechanism assumptions, including those expected to be more conservative such as missing not at random, to explore the robustness of any treatment effect, utilizing multiple imputation approaches. Full details of the sensitivity analyses will be pre-specified in the SAP.

Analyses of secondary endpoints

All secondary continuous efficacy endpoints will be summarized by visit and treatment group. In addition, the changes from baseline at scheduled visits in DSS score, SNOT-22 total score, Lund Mackay scores, sinus severity score, Zinreich score, individual NPSD scores, TSS, UPSIT, SF-36v2 (PCS, MCS, and domains), will be analysed using a ANCOVA, which is similar to the model used for the co-primary endpoints.

Time to first CRSwNP surgery up to Week 56, time to first course of SCS use for CRSwNP up to Week 56, and the time to first CRSwNP surgery and/or first course of SCS use for CRSwNP up to Week 56 will be analysed using a Cox proportional hazard model with treatment, region, and baseline CCI status CCI) as covariates.

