3.2 Demographics and baseline characteristics

Following demographics and key subject baseline variables will be provided. Baseline definition is specified in Section 3.1.3.

- Age
- Gender
- Country
- Region
- Race
- Ethnicity
- Weight
- Height
- BMI
- Nicotine use
- Nicotine consumption

Important baseline variables for CRSwNP and respiratory disease characteristics will be provided including but not limited to:

- number and percentage of subjects with prior surgery for CRSwNP
- number of prior surgery for CRSwNP
- number and percentage of subjects with prior SCS use for CRSwNP
- number of SCS use for CRSwNP in the past 12 months
- JESREC (<11 vs \geq 11)
- any aspirin exacerbated respiratory disease (AERD)/nonsteroidal anti-inflammatory drug exacerbated respiratory disease (NERD)
- CCI
- baseline blood eosinophil count
- atopic disease CCI
- anosmia (based on UPSIT \leq 18)

Important baseline variables for asthma disease characteristics will be provided including but not limited to:

- number of prior asthma exacerbations in the past 12 months
- number of prior SCS use for asthma in the past 12 months
- number of emergency room visit due to asthma in the past 12 months
- number of hospitalization due to asthma in the past 12 months
- baseline ACQ-6 score
- number and percentage of subjects using any ICS component (including maintenance and as needed use) at baseline
- number and percentage of subjects on maintenance ICS at baseline
- total daily ICS dose for asthma maintenance medications at baseline

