4.2.7.2 SCS use for CRSwNP and proportion of surgery for CRSwNP

At the primary DBL, surgery and SCS use for CRSwNP will be summarised during DB period for all patients in the PFAS. Specifically, the surgery for CRSwNP will be summarised by the surgery reason, and surgery procedures. The total number of courses of SCS use for CRSwNP, the total SCS dose for CRSwNP used, and total duration of SCS use for CRSwNP will be summarised using descriptive statistics. Each of these two events will be summarised regardless of if a patient experiences the other event (surgery for CRSwNP regardless of patient initiates SCS use for CRSwNP and vice versa).

The proportions of patients who had surgery and/or SCS CRSwNP listed in Section 3.5.2 will be summarised and analysed using the Cochran–Mantel–Haenszel (CMH) test stratified by region, CCI. The results of the analyses will be presented as odds ratios with associated 95% CI and 2-sided p-value.

The total number of courses of SCS use for CRSwNP will be analysed using a negative binomial model. All courses of SCS use during the double blind period defined in Section 3.1.1 will be included in the analysis. The response variable in the model will be the number of courses of SCS use for CRSwNP for each patient. The model will include covariates of treatment group, region, CCI and prior use of SCS for CRSwNP (yes vs no) as covariates. The logarithm of the patient's corresponding follow-up time will be used as an offset variable in the model. Marginal standardization methods will be used on the model estimates for all negative binomial analyses, unless otherwise specified.

As supportive analyses, the proportion of patients who potentially need surgery for CRSwNP ($NPS \geq 5$ and bi-weekly mean $NBS \geq 1.5$) during the DB period will be analysed using a similar CMH test as above.

At the final DBL, additional descriptive summary for surgery and SCS use for CRSwNP in the OLE period will be provided based on the OLE analysis set.

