4.2.9.2 Asthma exacerbation rate

The number of exacerbations associated with SCS use, hospitalisation, ER visit, and urgent care visit will be summarised by treatment group during DB period for all patients in PFAS, and during OLE period for patients included in OLE analysis, respectively.

The annual exacerbation rate (as defined in Section 3.7.2) during the DB period will be analysed using a negative binomial model. The response variable in the model will be the number of asthma exacerbations experienced by a patient during the DB period. The model will include covariates of treatment group, region, CCI [REDACTED] and number of prior exacerbations as covariates. The logarithm of the patient's corresponding follow-up time during the DB period will be used as an offset variable in the model to adjust for patients having different exposure times during which exacerbations could occur. Marginal standardisation methods will be used on the model estimates for all negative binomial analyses, unless otherwise specified.

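### The Cox models for surgery and SCS rescue omit baseline severity and rescue history that the trial collects; this costs some power but does not affect validity

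*SAP*

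**What the plan says.** SAP 4.2.7.1 states that time to first surgery, to first SCS course and to the first of either "will be analysed using a Cox proportional hazards model with treatment arm, region" and one redacted term. The supportive analysis of time to the surgery decision uses the same model. Protocol 9.4.1.2 specifies a "Cox proportional hazard model with treatment, region, and baseline CCI status", and protocol 4.1 says "Patients will be stratified by region and baseline CCI". The redacted term is therefore the second stratification factor, and the Cox models contain treatment and the stratification factors only. The redaction itself is not a gap.

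The negative binomial model for SCS courses (SAP 4.2.7.2) has treatment, region, the redacted factor "and prior use of SCS for CRSwNP (yes vs no) as covariates". It also states: "The logarithm of the patient's corresponding follow-up time will be used as an offset variable in the model". Estimates are marginally standardised.

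SAP 3.2 lists prior surgery (any, and how many), prior SCS (any) and the "number of SCS use for CRSwNP in the past 12 months" among the baseline variables. The asthma exacerbation model in SAP 4.2.9.2 has treatment, region, the redacted factor "and number of prior exacerbations as covariates".

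**The concern.** The documents themselves link the omitted variables to rescue. Inclusion criterion 5 uses NPS and nasal blockage to define severity that warrants surgery. A supportive analysis in SAP 4.2.7.2 classes a patient as potentially needing surgery when NPS is at least 5 and bi-weekly mean NBS is at least 1.5. Prior surgery and prior SCS use are pre-specified subgroup factors (SAP 4.2.5.3). The values should be nearly complete, because a qualifying NPS and at least 8 evaluable diary days are conditions of randomisation. The exacerbation model already adjusts for a count of earlier events, and no reason is given for handling rescue differently.

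Leaving a prognostic variable out of a Cox model moves the estimated hazard ratio towards 1 and loses power. Reduced need for surgery is part of the study rationale (protocol 2.1), and rescue supplies several secondary endpoints. No power is stated for any of them.

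**Working it through.** **The plan's own power figure.** SAP 1.4 gives 125 per arm, SD 2 (NPS) and 1 (NBS), differences 0.85 and 0.4, two-sided 0.05, overall power 80%.

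- NPS: 0.85 / (2 × √(2/125)) = 3.36; power = Φ(3.36 − 1.96) = 91.9%.
- NBS: 0.4 / √(2/125) = 3.16; power = Φ(3.16 − 1.96) = 88.5%.
- Product, treating the two as independent: 0.919 × 0.885 = 81.4% (81.0% with the noncentral t).

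The stated figure is reproduced. It is the only power figure in either document and says nothing about rescue.

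**Baseline power for rescue.** Schoenfeld's formula for 1:1 allocation is Φ(√events / 2 × |ln HR| − 1.96). With an assumed HR of 0.60, |ln HR| = 0.511:

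- 40 events: Φ(3.162 × 0.511 − 1.96) = 37%
- 60 events: 51%
- 80 events: 63%
- 100 events: Φ(5 × 0.511 − 1.96) = 72%

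**Effect of omitting a covariate.** Simulated trials had 250 patients, 1:1, exponential event times, censoring at the end of the double-blind period and no dropout. The log hazard was ln(0.60) × treatment + γ × x, with x standard normal. The baseline hazard was set so that placebo risk equals the target. Each trial was fitted by Cox regression without and with x, using a Wald test at 1.96. There were 2,000 runs per scenario, repeated with HR = 1 for type I error. All inputs except the sample size, allocation and alpha are assumptions.

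| Placebo risk | γ per SD | Mean events | HR without / with x | Power without / with x | Difference (points) |
|---|---|---|---|---|---|
| 20% | 0.3 | 41 | 0.601 / 0.598 | 33.3 / 33.0% | −0.3 |
| 20% | 0.5 | 41 | 0.600 / 0.593 | 34.2 / 35.3% | 1.1 |
| 20% | 0.8 | 41 | 0.611 / 0.591 | 31.7 / 36.6% | 4.9 |
| 35% | 0.3 | 72 | 0.601 / 0.596 | 56.3 / 56.7% | 0.4 |
| 35% | 0.5 | 73 | 0.610 / 0.597 | 53.3 / 56.4% | 3.1 |
| 35% | 0.8 | 74 | 0.624 / 0.589 | 50.5 / 58.9% | 8.4 |
| 50% | 0.3 | 106 | 0.605 / 0.599 | 72.0 / 74.2% | 2.2 |
| 50% | 0.5 | 106 | 0.620 / 0.599 | 67.9 / 74.3% | 6.4 |
| 50% | 0.8 | 108 | 0.647 / 0.599 | 59.8 / 74.2% | 14.4 |

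The Monte Carlo standard error of one power estimate is at most √(0.25/2000) = 1.1 points, so differences near zero should be read as zero. Type I error ranged from 4.2 to 5.8% across both models.

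The simulation contains neither region nor the redacted factor. If those already carry prognostic information, the gain from further covariates is smaller. Nothing was simulated for the negative binomial model, so no size is claimed for that part.

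**The case against.** The planned Cox models are coherent. They adjust for the randomisation factors, match the Cochran–Mantel–Haenszel tests on the same rescue endpoints and follow the protocol. The baseline-adjusted ANCOVA and logistic models are an imperfect precedent, because they use the baseline value of the same endpoint and time to surgery has none. Entry criteria restrict NPS to 5–8 and bi-weekly NBS to 1.5–3 and require prior SCS and/or surgery in everyone. That narrows the spread of the candidate covariates and makes the strongest scenarios harder to support. The endpoints are outside the multiplicity-controlled family (protocol 9.4.4). All of this stands and limits the size of the point. It does not remove a gain that can be pre-specified at low cost.

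A reader might infer three stronger things that the documents do not support.

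- That the negative binomial model ignores rescue history. It does not, since prior SCS use is a covariate.
- That the yes/no SCS term is uninformative because nearly everyone would be a yes. Criterion 5 admits patients with surgery only, and no distribution is given. A 12-month count also scores older users as zero, like never-users, so it complements the indicator and cannot replace it.
- That the planned hazard ratio is biased. The shift is non-collapsibility: the two models estimate effects conditional on different covariates.

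**Conclusion.** The rescue Cox models omit baseline severity and rescue history that the trial collects. The negative binomial model has prior SCS (yes/no) but lacks the number of recent uses and baseline severity. The consequence is lost efficiency on secondary endpoints. Under the assumptions above the Cox loss is about 0 to 14 points of power, with the hazard ratio up to about 0.05 closer to 1. The loss is 3 points or less for a weak covariate, at most 5 when rescue is uncommon (20%), and largest when rescue is common and the covariate strong. The actual size cannot be derived from the documents. The tests remain valid as planned, with simulated type I error of 4 to 6% with or without adjustment.

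**What to change.** Make these changes before unblinding:

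- **Cox models for time to first SCS and for the composite (SAP 4.2.7.1):** add baseline total NPS, baseline bi-weekly mean NBS and prior CRSwNP surgery (yes/no).
- **Cox models for surgery alone and for time to surgery decision:** leave unchanged. Surgeries may be few, and fixing this now keeps the choice of covariates from depending on event counts.
- **Negative binomial model (SAP 4.2.7.2):** keep prior SCS (yes/no); add the 12-month count of SCS uses for CRSwNP and baseline total NPS.
- **Current models:** report them as supportive.
- **SAP Section 6:** it now declares no changes from protocol. Record the Cox change there, because protocol 9.4.1.2 names the Cox covariates. The protocol specifies no covariates for the SCS-course model.

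The cost is SAP text and a few extra model fits; no new data are needed. The downsides are that the Cox hazard ratio becomes conditional on more covariates, and that the analysis departs from the protocol's stated model, which the CSR must report (protocol 9.4).

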4.2.7.2 SCS use for CRSwNP and proportion of surgery for CRSwNP

At the primary DBL, surgery and SCS use for CRSwNP will be summarised during DB period for all patients in the PFAS. Specifically, the surgery for CRSwNP will be summarised by the surgery reason, and surgery procedures. The total number of courses of SCS use for CRSwNP, the total SCS dose for CRSwNP used, and total duration of SCS use for CRSwNP will be summarised using descriptive statistics. Each of these two events will be summarised regardless of if a patient experiences the other event (surgery for CRSwNP regardless of patient initiates SCS use for CRSwNP and vice versa).

The proportions of patients who had surgery and/or SCS CRSwNP listed in Section 3.5.2 will be summarised and analysed using the Cochran–Mantel–Haenszel (CMH) test stratified by region, CCI. The results of the analyses will be presented as odds ratios with associated 95% CI and 2-sided p-value.

The total number of courses of SCS use for CRSwNP will be analysed using a negative binomial model. All courses of SCS use during the double blind period defined in Section 3.1.1 will be included in the analysis. The response variable in the model will be the number of courses of SCS use for CRSwNP for each patient. The model will include covariates of treatment group, region, CCI and prior use of SCS for CRSwNP (yes vs no) as covariates. The logarithm of the patient's corresponding follow-up time will be used as an offset variable in the model. Marginal standardization methods will be used on the model estimates for all negative binomial analyses, unless otherwise specified.

As supportive analyses, the proportion of patients who potentially need surgery for CRSwNP ($NPS \geq 5$ and bi-weekly mean $NBS \geq 1.5$) during the DB period will be analysed using a similar CMH test as above.

At the final DBL, additional descriptive summary for surgery and SCS use for CRSwNP in the OLE period will be provided based on the OLE analysis set.

4.2.7.3 Nasal polyp symptom diary

The bi-weekly mean of NPSD (individual components) as well as the TSS and the corresponding changes from baseline will be summarised by treatment group and by time point using descriptive statistics for all patients in the PFAS.

The changes from baseline will be analysed using a similar ANCOVA analysis as described for the co-primary endpoints in Section 4.2.5.1. The ANCOVA analysis for the TSS and components of NPSD other than NBS and DSS will be done for the primary estimand only.

4.2.7.4 University of Pennsylvania smell identification test score

The UPSIT scores will be summarised and analysed overall as well as separately for men and women.

The change from baseline in UPSIT total score will be analysed using a similar ANCOVA analysis as the primary endpoints described in Section 4.2.5.1 for the primary estimand only. Shift table of the olfactory diagnosis categories between the baseline and Week 56 will be generated separately.

4.2.7.5 Sinus CT: Sinus severity score and Zinreich score

The sinus severity score (across all sinuses) and Zinreich total score and their changes from baseline will be summarised by treatment group and by time point using descriptive statistics for all patients in the PFAS.

The change from baseline in sinus severity score and Zinreich total score will be analysed using a similar ANCOVA analysis as described in Section 4.2.6.2.

4.2.7.6 Short form 36-item health survey, version 2

For the SF-36v2, the eight subscale scores, the two component scores and their changes from baseline will be summarised by treatment group and by visit using descriptive statistics for all patients in the PFAS.

The responder (as defined in Section 3.5.7) rate at Week 24 and Week 56 will be summarised and analysed using the logistic regression with treatment arm, baseline from the corresponding SF-36v2 item, region, CCI [REDACTED] as covariates. Observed data will be used; subjects with missing or non-evaluable observations at the timepoint of interest are counted as non-responders.

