The proportions of responders at selected timepoints in total NPS and SNOT-22 total score will be analysed using logistic regression with treatment arm, baseline scores of corresponding endpoint, region, and baseline CCI status CCI) as covariates.

The proportion of patients who had CRSwNP surgery, the proportion of patients who had SCS for CRSwNP, and the proportion of patients who had CRSwNP surgery and/or SCS for CRSwNP up to Week 56 will be analysed using a Cochran–Mantel–Haenszel test controlling for region, and baseline CCI status CCI).

Analyses of pharmacokinetic variables

Benralizumab serum concentrations will be summarized using descriptive statistics. The population PK analysis will be presented separately from the main CSR.

Analyses of immunogenicity variables

Anti-drug antibodies status and the titers will be summarized using descriptive statistics. The impact of ADA on PK and eosinophil level will be assessed. The potential association of ADA with safety and efficacy will also be evaluated.

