1. STUDY DETAILS

1.1 Introduction

This is the statistical analysis plan (SAP) for study D3252C00002 and outlines the analyses to be generated for the global clinical study report (CSR). The SAP describes the statistical analyses specified in the latest version of the clinical study protocol (CSP) in more detail. Any changes to what is specified in the CSP will be described. Additional analyses required for regional submissions may be prespecified in separate documents and will be submitted to the appropriate authorities.

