To assess the effect of genetic variation on patient's response to therapy, susceptibility to, and severity and progression of disease	
 • A blood sample for deoxyribonucleic acid (DNA) isolation will be collected from patients who have consented to participate in the exploratory genetic analysis component of the study
To evaluate the effect of benralizumab on unplanned health care resource utilization	
 • Hospitalizations, emergency room and urgent care visits

[a] Treatment condition for primary estimand: Treatment with benralizumab versus placebo, regardless of compliance, where rescue with surgery and/or SCS for CRSwNP represents failure.
 
[b] Key secondary efficacy endpoints. A similar estimand as outlined for the co-primary endpoints will be used for analyses of repeated measures secondary endpoints. Co-primary and key secondary endpoints are multiplicity protected.
	

Table 2 Objectives and endpoints during the open-label extension (OLE)

Primary objective:	Endpoint/Variable:
To assess the safety and tolerability of benralizumab in patients with Chronic Rhinosinusitis with Nasal Polyps	
Safety and tolerability will be evaluated in terms of adverse events (AE)s, Vital signs, and Clinical laboratory.
 
 • Assessments related to AEs cover 
 - Occurrence/Frequency - Relationship to investigational product (IP) as assessed by investigator - Intensity - Seriousness - Death - AEs leading to discontinuation of IP

	
 • Vital signs parameters include systolic and diastolic blood pressure, and pulse. Assessments cover 
 - Observed value - Absolute change from baseline values over time • Laboratory variables
Secondary objectives:	Endpoint/Variable
To characterize the PK and immunogenicity of benralizumab	
 • PK: Serum trough concentrations • Immunogenicity: Anti-drug antibodies
Exploratory objectives:	Endpoint/Variable
Nasal polyp surgery	
 • Proportion of patients with surgery for CRSwNP
SCS use for relief of nasal symptoms	
 • Proportion of patients with SCS use for CRSwNP • Number of courses of SCS for CRSwNP • Total SCS dose used and total duration of SCS use for CRSwNP

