3.5.7 Short form 36-item health survey, version 2 (SF-36v2)

The short form 36-item health survey, version 2 (standard recall) (SF-36v2) is a 36-item, self-report survey of functional health and well-being, with 4-week recall period ([Quality Metric 2011](#)). Responses to 35 of the 36 items are used to compute an 8-domain profile of functional health and well-being scores. The remaining item, referred to as the ‘health transition’ item, asks patients to rate how their current state of health compared to their state of health 1 year ago, and is not used to calculate domain scores. The 8-domain profile consists of the following subscales: physical functioning (PF), role limitations due to physical health (RP), bodily pain (BP), general health perceptions (GH), vitality (VT), social functioning (SF), role limitations due to emotional problems (RE), and mental health (MH). Psychometrically based physical and mental health component summary scores (PCS and MCS, respectively) are computed from subscale scores to give a broader metric of physical and mental HRQL.

Categorical analyses will be conducted to evaluate treatment impact on the basis of the established threshold values for change for each scale. The SF-36v2 threshold listed in [Table 9](#) is suitable for interpreting change at the individual level and is referred to as the responder threshold or responder definition ([Quality Metric 2011](#)). SF-36 responders, defined as change \geq threshold noted in [Table 9](#), will be derived using the approach mentioned in [Section 3.1.5](#), regardless of surgery or SCS use for CRSwNP.

Table 9 Threshold values for the SF-36v2 scale and summary measures

	SF-36v2 score									
Threshold	PCS	MCS	PF	RP	BP	GH	VT	SF	RE	MH
Individual change	3.4	4.6	4.3	3.4	6.2	7.2	6.2	6.9	4.5	6.2

BP=Bodily Pain; GH=General Health Perceptions; MCS=Mental Health Component Summary; MH=Mental Health; PCS=Physical Component Summary; PF=Physical Functioning; RE=Emotional Problems; RP=Role Limitations due to Physical Health; SF=Social Functioning; VT=Vitality.

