6. CHANGES OF ANALYSIS FROM PROTOCOL

Not applicable.

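### The SAP drops the protocol's ANCOVA of change in SF-36v2, the only one of nine listed endpoints to lose it, and its section on changes from the protocol does not say so.

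*SAP*

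**What the plan says.** Protocol 9.4.1.2, on secondary endpoints, lists the changes from baseline that receive a model similar to the co-primary one. The list ends "individual NPSD scores, TSS, UPSIT, SF-36v2 (PCS, MCS, and domains), will be analysed using a ANCOVA". The same section limits its logistic responder analyses to two endpoints: "The proportions of responders at selected timepoints in total NPS and SNOT-22 total score will be analysed using logistic regression".

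SAP Table 1 keeps change from baseline in SF-36v2 PCS, MCS and domains as the endpoint for the general-health secondary objective. Footnote b of that table says: "A similar estimand as outlined for the co-primary endpoints will be used for analyses of repeated measures secondary endpoints".

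SAP 4.2.7.6 then gives two analyses for SF-36v2. For the eight subscales, "the two component scores and their changes from baseline will be summarised by treatment group and by visit using descriptive statistics". For responders at Weeks 24 and 56 there is a logistic regression, with missing values counted as non-response. SAP 3.5.7 derives those responders "regardless of surgery or SCS use for CRSwNP".

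On disclosure, SAP 1.1 promises: "Any changes to what is specified in the CSP will be described". SAP Section 6 reads in full "Not applicable".

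**The concern.** The protocol and the SAP disagree on how a named secondary endpoint is analysed, and the SAP states that nothing has changed. If the SAP is followed, the study report will show by-arm summaries of SF-36v2 change and a set of odds ratios, but no pre-specified adjusted mean difference with a confidence interval.

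The odds ratios do not stand in for that estimate. They answer a question about crossing a threshold, they discard part of the information in the score, and they treat surgery and systemic corticosteroid rescue differently from the rest of the efficacy plan. A reader who relies on Section 6 would not know that a protocol-specified analysis had been removed and another put in its place.

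**Working it through.** **1. Match each endpoint in the protocol sentence to its SAP section.**

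| Endpoint in Protocol 9.4.1.2 | SAP section | ANCOVA of change kept? |
|---|---|---|
| DSS | 4.2.6.1 | yes |
| LMS | 4.2.6.2 | yes |
| SNOT-22 | 4.2.6.3 | yes |
| Individual NPSD scores | 4.2.7.3 | yes |
| TSS | 4.2.7.3 | yes |
| UPSIT | 4.2.7.4 | yes |
| Sinus severity score | 4.2.7.5 | yes |
| Zinreich score | 4.2.7.5 | yes |
| SF-36v2 (PCS, MCS, domains) | 4.2.7.6 | **no** |

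Eight of nine keep the model. UPSIT, a non-key secondary endpoint like SF-36v2, is the closest comparison: "The change from baseline in UPSIT total score will be analysed using a similar ANCOVA analysis as the primary endpoints".

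**2. Look for the model elsewhere in the SAP.** Section 4.1 and Table 11 cover the co-primary and key secondary endpoints only. Section 3.5.7 plans categorical analyses. Appendix 8.10 has no SF-36v2 row. Table 14 (random seeds) has a row even for the CT endpoints, marked NA, but none for SF-36v2. Table 13 lists worst-possible values for all ten SF-36 scores, which no stated SF-36v2 analysis uses.

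**3. Look for a declaration.** Section 6 declares nothing. The SAP amendment entry of 14 January 2024 records the removal of some supportive analyses and shift plots in Sections 4.2.6 to 4.2.7. It names neither SF-36v2 nor an ANCOVA.

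**4. Count what is missing.** PCS, MCS and 8 domains give 10 adjusted mean differences at Week 56. What remains is 10 scores × 2 time points (Weeks 24 and 56) = 20 responder odds ratios.

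**5. Illustrate the cost of dichotomising.** The documents give no SD, expected effect or response rate for SF-36v2, so these inputs are assumed: normal change with equal SD in both arms, 125 patients per arm (250 randomised 1:1), two-sided 0.05, no covariates, rescue and missing data not modelled.

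The information kept when a normal variable is split so that a proportion p respond is φ(z_p)² / [p(1 − p)]:

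| p | kept | of 250 patients |
|---|---|---|
| 0.2 | 0.490 | about 122 |
| 0.3 or 0.7 | 0.576 | about 144 |
| 0.4 or 0.6 | 0.622 | about 155 |
| 0.5 | 0.637 | about 159 |

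For the t-test, the non-centrality is d√(125/2): 2.372 at d = 0.3 SD and 3.162 at d = 0.4 SD. For the responder test, the active-arm rate is Φ(z_p + d), where p is the placebo rate, and power comes from log OR / SE. Worked case, p = 0.2 and d = 0.3: the active rate is 0.294, log OR 0.510, SE 0.298 and ratio 1.715, so power is Φ(1.715 − 1.960), or about 0.40.

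| Difference | t-test | Responder test, placebo rate 0.2 / 0.3 / 0.4 / 0.5 |
|---|---|---|
| 0.3 SD | 0.656 | 0.404 / 0.449 / 0.467 / 0.465 |
| 0.4 SD | 0.883 | 0.633 / 0.686 / 0.703 / 0.697 |

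A simulation of 20,000 runs at 0.4 SD agrees: t-test 0.88 to 0.89; responder test 0.65, 0.69 and 0.70 at placebo rates of 20%, 30% and 50%.

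**The case against.** The omission itself is not open to dispute. The case against making more of it has several parts.

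- **The responder analysis was foreseeable.** Protocol 8.1.1.3 and Table 9 give responder thresholds for all ten scores, and the SAP log mentions the SF-36 responder definition. This is true, but Protocol 9.4.1.2 plans no responder model for SF-36v2, and thresholds do not replace the planned ANCOVA.
- **Footnote b is attached to the key secondary endpoints.** Its superscript sits on DSS, LMS and SNOT-22, and a note to Table 11 says estimand attributes are spelled out only for primary and key secondary endpoints. That weakens the footnote as a complete specification. Its wording still reaches repeated-measures secondary endpoints in general, and SF-36v2 is one. SAP 3.1.5 allows exceptions to the rescue rule for responders, so ignoring rescue there is a choice, not an error.
- **The difference is recoverable.** By-arm means and SDs will be reported, so an unadjusted difference can be calculated afterwards. That stands. What is lost is the pre-specified, covariate-adjusted estimate with rescue handled as elsewhere.
- **The power figures rest on assumed inputs and a normal model.** Worst-possible imputation would not produce normal data. This also stands; the figures illustrate the loss and the finding does not depend on them.
- **Tables 13 and 14 are imperfect evidence.** Table 14 still holds seeds for ACQ-6, which no longer uses multiple imputation. Both tables are therefore minor support only.
- **Disclosure could come later.** Protocol 9.4 says deviations will be reported in the study report. That does not make the current Section 6 correct.

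**Conclusion.** The concern holds. One of nine endpoints loses its protocol-specified ANCOVA, ten adjusted mean differences at Week 56 go unplanned, and Section 6 is wrong in stating that there is nothing to report. It is wrong on a second count as well: Protocol 9.4.3.1 plans a co-primary-type ANCOVA for ACQ-6 (exploratory), while SAP 4.2.9.1 uses a repeated-measures model under a treatment-policy estimand.

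Under the stated assumptions, dichotomising keeps 49% to 64% of the information, and power falls from 66% to 40–47% at 0.3 SD and from 88% to 63–70% at 0.4 SD.

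The consequence is confined to a secondary endpoint outside the hierarchy in SAP 4.1.3. Type I error control and the co-primary and key secondary results are untouched. This should be corrected, but it does not threaten the main conclusions.

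**What to change.** 1. In SAP 4.2.7.6, restore the ANCOVA of change from baseline for PCS, MCS and the eight domains, handled as for UPSIT: worst-possible value after surgery (from Table 13), worst observation carried forward after systemic corticosteroids for CRSwNP, and multiple imputation for other missing data. Report the LS mean difference and 95% CI at Week 56.
2. Add ten pairs of SF-36v2 seeds to Table 14.
3. Keep the responder analysis as supportive and label it as treatment policy for rescue.
4. In Section 6, replace the present entry with a list that declares the added SF-36v2 responder analysis and the ACQ-6 model change, each with its reason.

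If the sponsor did intend to remove the SF-36v2 ANCOVA, the minimum is to declare and justify that in Section 6 and delete the unused SF-36 rows of Table 13. This is the weaker option, because the listed endpoint would still have no adjusted estimate.

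The cost is SAP wording, the seeds, and re-use of existing imputation and ANCOVA programs. No new data are required.
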